5.8 Methods and Timing for Assessing, Recording, and Analyzing Safety Parameters

Serious adverse events and deaths will be recorded and reported to the NIA and DSMB within 48 hours of occurrence (or when the clinical staff become aware of the occurrence). Full descriptions of the serious adverse event and deaths will be made as soon as complete dossiers on the clinical information can be accumulated. Source documents from hospitalizations will be obtained in every case unless patient does not consent to do this. All reference to the patient will be redacted (name, names of relatives, date of birth, etc).

Stopping rule. A decision to discontinue the study will be based primarily on serious adverse events (SAEs). In discussion with the DSMB as it relates to timing of any decision making, the study will be stopped if unexpected and possibly study-related SAEs occur in 20% or more of the study population, or if an imbalance of these SAEs occur in 15% or greater of those participating in either treatment arm. We anticipate that unexpected and

possibly study-related SAEs will be rare, because participants will be receiving well tolerated antihypertensive therapies with substantial clinical safety oversight by the PI and research staff. Research nurses and staff who assist in the conduct of the trial will detect SAEs. In addition to the immediate disclosure, complete reports of SAEs will be reviewed at monthly staff meetings with the PIs, research nurses and physicians.

The NIH/NIA Adverse Events Monitoring Form will be used to collect detailed information about all serious adverse events, how they were handled, and their potential relationship to study participation. The procedures for SAE reporting also include written documentation using clinical notes related to the adverse event and specific forms detailing the event with a sign-off by clinical hypertension research MDs. Communication of recommendations and decisions from all parties (DSMB members, investigators, IRB) will be made in a timely manner as noted above. All of these individuals will receive a copy of the expected Serious Adverse Events Monitoring Form within 10 business days or sooner (48 hours) in the case of deaths and study-related SAES, at which point a decision will be made whether to convene a meeting.

Reviews of SAE and other safety data will be made at 4 month intervals by the DSMB members. Each DSMB member will vote on whether the study should: 1) continue as planned without changes; 2) continue after a protocol amendment; or 3) stop the trial pending further investigation. If, after this meeting, the DSMB votes to stop recruitment or requests a protocol modification due to concerns with patient safety, the IRB and NIH project officer will be informed immediately.

Other adverse events, such as cardiovascular, neurologic or renal adverse events not requiring hospitalization, will also be reported within 48 hours to the PIs by the study nurse and/or project manager. A determination of how to proceed will be made based on

consultation with the physician investigators on the project, or the patient's own physician, provided a release of information has been obtained. These adverse events will also be recorded on an Adverse Events Monitoring Form, which is similar to the SAE form.

A database of all adverse events will be maintained by the project manager in conjunction with the study nurse coordinator. Once per month, in research team meetings, all adverse events will be reviewed that occurred over the prior month, as well as over the course of the trial. In addition, the local IRB maintains records of all adverse events. Deaths and study related serious adverse events are reviewed immediately, and data are sent to NIH per standard policy. Aggregate data on reports of adverse events are reviewed on at least an annual basis by the IRB for study continuation, and at 4 month intervals by the external DSMB and study investigators. Any temporary or permanent suspension of patient accrual will be reported to the NIH project officer.

5.9 Reporting Procedures

Serious and non-serious adverse events will be documented as noted above and reported on a regular basis to the project director, the PI, the IRB, and NIA as indicated. Every 4 months, reports of aggregate data will be submitted to the data safety committee members that contain baseline demographics, retention data, adverse events and laboratory data, and any other data that will help in the assessment of the clinical trial. Based on this report, each DSM committee member will recommend on whether the study should: 1) continue recruitment unchanged; 2) continue with a protocol amendment; 3) stop recruiting pending further investigation. If, after this meeting, any DSM committee member votes to stop recruitment or requests a protocol modification, the IRB will be informed.

5.10 Follow-up for Adverse Events

Participants who experience a significant medical problem requiring an overnight hospitalization at an acute care facility will be defined as having experienced a serious AE, which are expected to occur fairly regularly in this age group. Types of SAEs in the hypertensive population with vascular disease are as follows: cardiovascular complications of hypertension including myocardial infarction, stroke, arrhythmias, and heart failure. Other non-serious adverse events (AEs), such as shortness of breath, dizziness, or near syncope not requiring hospitalization, will also be reported. All SAEs and AEs result in the completion of an Adverse Events Monitoring Form within 2 days of discovery to the PI and/or study coordinator by the research nurses and/or research assistants.

The Adverse Events Monitoring Form is adapted from one being used in the NIH Clinical Trials Network and our other ongoing trials. This form collects detailed information about all adverse events, how they were handled, and their potential relationship to study participation. The procedures for adverse event reporting also include written documentation using clinical notes related to the adverse event and specific forms detailing the event with a sign-off by all appropriate supervisory personnel.

We anticipate that unexpected and possibly study-related SAEs will be rare, because participants will be receiving well-tolerated, FDA approved pharmacotherapy. None of the study procedures are associated with SAEs.

As noted above, clinical research staff will review all past month and study cumulative AEs and SAEs at monthly meetings. All research staff members have completed required institutional training on research with Human Subjects. Research staff are trained in adverse event reporting and understand that their responsibility is to document and report adverse events reported by study participants, independent of determinations made at the time or later of the relationship between the event and participation in the study.

Adverse events will be followed until they are resolved or considered stable by the clinical investigative team. We have an AE/SAE log in every case report form that will be updated as the disposition of the adverse event evolves. The categories include a) resolved, b) reduced, c) unchanged.

5.11 Safety Monitoring

This study has a formal data safety monitoring plan and will be evaluated by an independent Data Safety Monitoring Board (DSMB) (see appended draft DSMB Charter).

6. INTERVENTION DISCONTINUATION

- A. Patients will be discontinued from their antihypertensive intervention if it is deemed that the treatment(s) or blood pressure level is no longer safe or appropriate based on clinical condition (e.g. development of congestive heart failure that mandates a specific regimen or development of a terminal malignancy).
- B. Potential reasons for discontinuation of the intensive treatment might include untoward symptoms associated with low blood pressure related to development of a new morbidity (e.g. blood loss, sepsis) or intolerance to therapy (e.g. lightheadedness/syncope. In rare cases, hyperkalemia or hyponatremia may develop that would be unmanageable under the constraints of the protocol-drive therapies. Hypokalemia will be managed with aggressive potassium replacement to maintain serum levels > 3.5 meq/L.
- C. As this is an intention-to-treat trial, patients who discontinue treatment interventions will be invited to participate in clinical follow-up and all comprehensive outcome studies at months 18 and 36 of the trial.
- D. In the event of temporary discontinuation of antihypertensive treatment (e.g. need to withhold antihypertensive medications due to surgery, post-operative bleeding, infection or other causes of low blood pressure), reassessment of these individual patients will be made

in the research clinic for a return of BP levels towards baseline, and study medications will then be resumed.

[figure not shown]
7. STATISTICAL CONSIDERATIONS

7.1 General Design Issues

General considerations: Predictor, covariate, and dependent variables will be examined for outliers and data beyond the range of human performance. We will analyze variables on the original measurement scale, or on a scale that allows meaningful interpretation e.g., when an inverse transformation on a time measure results in a speed interpretation. The primary analyses (hypotheses 1, 2 and 3) will be intention-to-treat.

Hypothesis models, analysis plan, and power estimates for primary outcomes were developed with PASS 2008³⁵ and SAS PROC POWER³⁶ were used for estimation of power.

8.2 Hypotheses and Statistical Analyses

The Figure shows graphically how our hypotheses relate to one another. Hypothesis 1 tests the combined effects of paths A, B, C, D & E i.e., the total effect of BP on mobility. Hypothesis 2 tests path A, Hypothesis 3 tests path D, Hypothesis 4 tests path B+E; together Hypotheses 2, 3 and 4 together test the effect of BP on mobility mediated through BP's effects on WMH and WM microstructure. Hypothesis 5 tests the relative importance of paths A and B to that of path C, i.e., the degree to which the effect of BP on mobility is explained by WMH. Hypothesis 6 tests the relative importance of paths D and E to that of path C, i.e., the degree to which the effect of BP on mobility is explained by changes in WM microstructure.

Hypothesis path diagram

Hypothesis 1: Intensively treating 24-h systolic BP to a goal of <130 mmHg versus standard BP control of <145 mmHg will lead to faster walking speeds at T₃₆. (Paths A&B+C+D&E)

Hypothesis 2: Intensively treating 24-h systolic BP to a goal of <130 mmHg versus standard BP

control <145 mmHg will lead to smaller total WMH volume. (Path A)

Hypothesis 3: Intensively treating 24-h systolic BP to a goal of <130 mmHg versus standard BP

control <145 mmHg will stabilize brain WM microstructural integrity (FA and MD) at T₃₆. (Path

D) We will perform 3 sets of analyses for hypotheses 1, 2 & 3:

- a. Multiple linear regression will be performed with treatment group (intensive vs. standard) as the predictor of interest. Gait velocity at T₃₆ is the primary outcome for hypothesis 1, WMH at T₃₆ is the primary outcome for hypothesis 2, and DTI indices (FA and MD) are the primary outcomes for hypothesis 3. The analysis will be intention-to-treat. Age, sex, and 24 hour SBP at T₀ (baseline) will be included as covariates, along with other demographic factors for which the treatment groups are not comparable. **The analysis for hypothesis 1 is the proposal's primary efficacy analysis and thus the proposal is powered to address this analysis (see Sample size estimation).**
- b. We will repeat analyses 1a, 2a and 3a but with gait velocity at T₁₈, total WMH at T₁₈, and DTI indices at T₁₈ as the primary outcomes. A comparison of these analyses with analyses 1a and 1b will determine the time course of the intervention's effects. In particular, it will be important to determine if these effects occur early (T₁₈) or require a 3-year treatment period. In addition, for participants who are present at T₁₈ but not T₃₆, the data from T₁₈ will be used to estimate the effect of informative loss to follow-up. (See Missing Data)
- c. We will further examine the progression of mobility and WMH changes using a progression model using methods adapted from Diggle:³⁶

$$Y_{i0} = b_{i0} + \beta_T (X_i) + \text{cross sectional covariates} + \text{residual error}$$

$$Y_{i18} = b_{i0} + \beta_T (X_i) + \beta_L + \beta_E (X_i) + \text{cross sectional covariates} + \text{longitudinal covariates} + \text{residual error}$$

$$Y_{i36} = b_{i0} + \beta_T (X_i) + \beta_L^* + \beta_E^* (X_i) + \text{cross sectional covariates} + \text{longitudinal covariates} + \text{residual error}$$

Here, Y_{i0} , Y_{i18} , and Y_{i36} are the outcomes (mobility or imaging) at T_0 , T_{18} , and T_{36} for study participant i , and X_i is the treatment group assignment indicator for study participant i , and b_{i0} is a random intercept used to account for the fact that repeated measurements on individuals are not independent; the other β_j 's are fixed effects in this example although we will consider the possibility that treating them as random effects will add to the model fit. The model will be fit as a linear mixed model.^{37, 38} The parameters of interest are β_E , and β_E^* , the difference in the outcome progression rate (mobility or imaging) between the treatment groups at T_{18} and T_{36} . If the difference in the rate of progression is constant during follow-up, we would expect β_E^* to approximately equal $2 \times \beta_E$. This allows a more powerful and rigorous test of whether the intervention's effects are manifested quickly or over the long-term. Additional secondary analyses will use the T_{18} data to determine temporal continuity of the trends and as a partial assessment of the effect of dropout. Additional secondary analyses will use logistic regression with severity of urinary incontinence at T_{36} and T_{18} as an ordinal outcome.

Other mobility measures will also be examined as secondary outcomes in models otherwise identical to those in a, b, and c. The analyses will be repeated for cognition, with the speed obtained on Trailmaking B at T_{36} as the primary outcome and other cognitive measures as secondary outcomes. Additional secondary analyses will use logistic and ordinal models with the same predictors and incontinence presence and severity, respectively as outcomes; the progression model (c) will be fit as binary or ordinal generalized linear mixed models.

Hypothesis 4: Reduced total WMH and decreased markers of tissue damage on DTI at T_0 and at T_{36} are linked to better mobility at T_{36} . (Paths B+E)

The same outcomes will be used for this hypothesis as in hypothesis 1, with identical analyses except that WMH, and DTI indices (FA and MD) as continuous variables will be the primary predictor of interest. The power for this hypothesis as expressed as increased in explained variability (R^2) will be the same as for hypothesis 1: 85% power to achieve an increase in R^2 of 0.0533; we actually observed an increase in R^2 of 0.1658, to 0.2925, as the effect of tWMH, corresponding to a reduction in gait

velocity of 0.0063 m./sec. for each 0.1% increase in tWMH. The analyses will be repeated for gait velocity at T₁₈ with a model corresponding to analysis b, and for the following progression model replacing the model for analysis c:

$$Y_{i0} = b_{i0} + \beta_C (X_{i0}) + \text{cross sectional covariates} + \text{residual error}$$

$$Y_{i18} = b_{i0} + \beta_C (X_{i0}) + \beta_L (X_{i18} - X_{i0}) + \text{cross sectional covariates} + \text{longitudinal covariates} + \text{residual error}$$

$$Y_{i36} = b_{i0} + \beta_C (X_{i0}) + \beta_L (X_{i36} - X_{i0}) + \text{cross sectional covariates} + \text{longitudinal covariates} + \text{residual error}$$

Here, Y_{i0} , Y_{i18} , and Y_{i36} are the outcomes (mobility or imaging) at T₀, T₁₈ and T₃₆ for study participant i , X_{i0} , X_{i18} , and X_{i36} the tWMH at T₀, T₁₈ and T₃₆ for study participant i , and b_{i0} is a random intercept that is used to take into account the fact that repeated measurements on individuals are not independent. The model will be fit as a linear mixed model³⁷. Again the other β_j 's are fixed effects although we will consider the possibility that treating them as random effects will add to the model fit. The parameters of interest are β_C and β_L , the cross-sectional and longitudinal effects of the imaging measures on mobility over the 36-month follow-up. As secondary analyses we will consider interactions with treatment group and nonlinear effects in time. Analyses will be repeated for the other mobility and cognitive measures, also as linear mixed models, and urinary incontinence presence/severity as binary and ordinal generalized linear mixed models.

Hypothesis 5: Total WMH at T₀ and at T₃₆ mediate the effect of treatment group, showing that

the mechanism by which reduced ABP is linked to better mobility occurs by reducing total WMH.(Paths C - A&B) Mediation models allow the evaluation of hypotheses using biological mechanisms. In this case, we believe that much of the salutary effect of reduced ABP results from reduced WMH. Assessing mediation involves estimating direct effects (Path C, above) and indirect effects (Paths A and B, above) in multistage predictor models by adding potential mediators to models describing the effect of a predictor on the outcome. To the extent by which WMH mediates the effect of BP, the effect of BP will be reduced in the model that includes WMH compared to the model not including WMH. We saw this in our observational study, as the adjusted effect of SBP in the pseudo-treatment group was reduced

from a .15 m/sec. to a .1 m/sec. difference in gait velocity when WMH was added as a model predictor.

Product of coefficients methods^{35,36} will be used for formal statistical inference regarding the mediation. Specifically, we will estimate the product of the effect estimated for hypothesis 2 corresponding to Path A (the effect of intervention group on total WMH at T₃₆), and the effect estimated for hypothesis 3 corresponding to Path B (the effect of WMH at T₃₆ on gait velocity at T₃₆). The magnitude of this product turns out to be proportional to the change in the effect of intervention group on gait velocity at T₃₆ when WMH at T₃₆ is added to a regression model of gait velocity at T₃₆ as a function of intervention group. Similar models will be used to assess outcomes at T₁₈, and the cognitive outcomes. As formal tests for mediation using the product of coefficients method require larger sample sizes than available in this study, we will treat results from analyses in Hypothesis 5 as preliminary, to be potentially verified by a larger study should the main effects in Hypotheses 1-3 be confirmed.

Hypothesis 6: Diffusion tensor imaging (DTI) indices (FA, MD) at T₀ and at T₃₆ mediate the effect of treatment group, showing that the mechanism by which reduced ABP is linked to better mobility occurs by preserving brain WM microstructural integrity (FA, MD).

(Paths C – D&E) The same analysis as used for hypothesis 5, except that the mediating effect of the DTI indices will be assessed.

Missing Data.

Death and study attrition are associated with age-related diseases. Failure to account for this informative censoring may result in biased estimates of dementia risk and cognitive decline.³⁷ Hence, we will collect data by telephone to assess the degree to which living participants who fail to appear for their final assessment differ from participants who complete the study. As mentioned above, we will use telephone administration of a validated mobility assessment³⁹ and the method developed by [name] and colleague³⁰ to estimate mobility outcomes through multiple imputation or joint modeling that would have been

observed had the participants appeared for their clinical assessment. While our primary efficacy outcome analysis will be limited to participants who complete the study, this will be the first trial in aging with the potential to assess the impact of informative dropout beyond usual sensitivity analyses.

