12. PUBLICATION OF RESEARCH FINDINGS	39
13. REFERENCES	39
14. SUPPLEMENTS/APPENDICES	Error! Bookmark not defined.

I. Procedures Schedule

II. Informed Consent Form (approved by UCHC IRB June 2011)

III. Other (*add as many appendices as necessary*)

PARTICIPATING STUDY SITES

This is a single-site trial, taking place at the University of Connecticut Health Center, located at [name].

PRÉCIS

Study Title

Intensive versus Standard Blood Pressure Lowering to Prevent Functional Decline in Older People

Objectives

The goal of this randomized clinical trial is to determine if lowering and maintaining 24-h ambulatory systolic BP (ABP) to ≤ 130 mmHg (*intensive control*) versus < 145 mmHg (*standard control*) slows/halts progression of deterioration of mobility and cognitive function linked to white-matter disease (also known as white-matter hyperintensity or WMH) in patients with normal or mildly impaired mobility and cognition in subjects with detectable cerebrovascular disease ($\geq 0.5\%$ WMH fraction of intracranial contents).

Design and Outcomes

The study is a single-site, prospective randomized, open-label trial with blinded endpoints (PROBE), in patients ages 75 and older with elevated 24-h systolic BP (> 150 mmHg in the untreated state) who do not have unstable cardiovascular disease, congestive heart failure or history of stroke.

The key primary and secondary outcomes in the trial are:

- 1) change from baseline in mobility parameters (self-paced walk and stance times)
- 2) change from baseline in cognitive function (executive function, processing speed)

- 3) Accrual of WMH over the course of the trial (36 months) including degeneration of tissue and tissue perfusion using an MRI technology known as diffusion tensor imaging (DTI)

Interventions and Duration

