5.6.2 Enrollment, Baseline, and/or Randomization

A. Enrollment Period

Baseline visit 1

- Fasting laboratory studies*
- Review and discussion of medication tapering if needed (by physician)
- Brief exam and standardized blood pressures
- Medical history, including evaluation of concomitant medications, adverse events for baseline
- **Laboratory Tests:** includes complete blood count, serum creatinine and blood urea nitrogen, glucose, ALT, urinalysis, total cholesterol, LDL and HDL cholesterol and triglycerides (fasting)
- **Baseline MRI** – (Radiology) Note: if patient has no WMH on baseline MRI, they will be excluded from further participation in the trial. No medication tapering will occur prior to the results of this study.

Baseline visit 2– this visit will be the first assessment following taper of prior antihypertensive therapy for those patients demonstrating WMH on the screening MRI.

- Medical history (intercurrent illnesses, medication history, adverse events)
- Standardized clinic BPs*

If patient is off antihypertensive agents at baseline or has been discontinued for 2 weeks with a mean clinic SBP \geq 150 mmHg, patient will proceed with various tests below. If SBP < 150 mmHg, patient will return in 1 week to re-evaluate clinic BPs.

- *Standardized clinic BP measurements will be taken using the validated Suntech Medical Instruments TM24/7 in the non-dominant arm, seated position in duplicate and 1 upon standing prior to dosing of morning BP medications.
- Ambulatory BP monitoring
- Home BP monitoring – self-monitoring with a portable digital device, obtaining BP readings twice-daily in duplicate (morning, evening) for seven days. Patients will receive training on proper use of the device and record readings on separate sheet. Blood pressure readings will be obtained in the seated position prior to any morning and/or evening antihypertensive medications.
- Mobility battery - Gait Speed, Stair ascent and descent, Supine-to-sit, Sit-to-stand, Functional reach, Stance time, Single leg stance
- Cognitive battery – HVLIT, Trail Making Test, Digit Span Test (Forward and Backward), Digit Span, Stroop Color and Word Test, Symbol Digit Substitution, Controlled Oral Word Association Test, California Computerized Assessment Package (Cal CAP), Geriatric Depression Scale.
- Incontinence questionnaires - UI 31Q, Urinary Incontinence Severity Index, Urogenital Distress Inventory (UDI), IIQ-7
- Mini-mental status exam

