8.3 Sample Size and Randomization

We conservatively estimate that at least 140 of the original 200 participants will complete assessments at 35 months. We analyzed a subset of participants in our earlier observational study in order to mimic the results of the two treatment groups we expect to see in the intervention study. For a standard care arm, we selected participants in the observational study who had 24 hour systolic BP between 140 and 150 mmHg, inclusive, at follow-up, and for the intensive treatment arm, we selected participants with 24 hour Systolic BP between 120 and 130 mmHg, inclusive, at follow-up. A regression of gait velocity over 8 feet on our covariates age, sex, and 24 hour systolic BP at baseline showed an r^2 of 0.1267. If we see similar results in the intervention study, 140 participants (70 in each group) will give us 85% power to observe an increase in r^2 of 0.0533 to 0.1800. In our prior observational study, we saw an increase in r^2 of 0.1082 to 0.2349, with a difference in gait speed between the two simulated treatment groups of 0.15m./sec. While the 0.15m/sec gait speed difference between the low and high BP groups appears small, it represents only 2 years of observation. Mobility impairment linked to WMH is a long-term decremental process that limits gait velocity over 10 or more years. Thus a “small” 2-year differential is both believable and meaningful. We are therefore confident that the proposed study has ample power to find smaller yet clinically significant effects for our primary outcome. A regression of total WMH on covariates age, sex, and 24 hour systolic BP at baseline showed an r^2 of 0.1162. Similar results in the intervention study imply 85% power to observe an increase in r^2 of 0.0540 for the effect of the treatment arm, to 0.1702. We actually observed an increase of 0.0861, to 0.2023, in the prior observational study, corresponding to a difference between the two simulated treatment groups of 0.93% total WMH.

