**Intensive Versus Standard Blood Pressure Lowering to Prevent
Functional Decline in Older People**

NCT01650402

Statistical Analysis Plan

IRB Approval Version 9/25/2018

INFINITY Statistical Analysis Plan (modification)

IRB Review
IRB NUMBER: IE-11-155S-2
IRB APPROVAL DATE: 09/25/2018

Principal Investigators: [name], [name]
Senior Statistician: [name]
Project Statistician: [name], MS
Date: 24 September 2018

Amendment 1.1

The primary objective of the INFINITY Trial is to assess causality between 24-hour systolic BP levels and preservation of mobility, cognitive and urinary function associated with reduced accrual of small vessel disease of the subcortical white matter in people over the age of 75 years.

A key hypothesis of the trial is that intensive treatment of 24-hour systolic BP to levels of 130 mmHg or less will result in improved gait time, stair descent time, and maximal gait velocity compared to treatment of 24 hour systolic BP to levels of 145 mmHg or less. This separation of ambulatory BP goals should achieve at least a ≥ 10 mmHg differences between groups over time. Previously, this difference has been shown to be responsible for the mobility decrements associated with WMH in older patients with systolic hypertension in a prospective cohort study (Circulation. 2011;124 (21):2312-9. doi: 10.1161/CIRCULATIONAHA.111.037036).

Prior to database lock of this trial in October 2018, we have added several secondary analyses to be pre-specified with their rationale as needed.

1. Change in white matter hyperintensity (%) (WMH) from baseline to 3 years
 - a. According to treatment group (primary analysis)

$$\begin{aligned} Y_{i1} &= \beta_0 + \beta_C x_i + \gamma_i + \varepsilon_{i1} \\ Y_{i2} &= \beta_0 + \beta_C x_i + \beta_L + \beta_T x_i + \gamma_i + \varepsilon_{i2} \end{aligned} \tag{1.1}$$

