Here, x_i is the treatment group indicator for participant i as in (1); Y_{i1} is the mobility score for participant i at time 1 (baseline); Y_{i2} is the mobility score for participant i at time 2 (36 month follow-up); β_0 is interpreted as the average mobility score at baseline in the reference group; β_C is interpreted as the difference in the average mobility score at baseline between the intervention group and the reference group and will be zero if the two groups are exactly comparable in their baseline values; β_L is interpreted as the average change in mobility between 36 month follow up and baseline in the reference group; β_T is interpreted as the difference average change in mobility between 36 month follow up and baseline between the intervention group and the reference group and thus the parameter of primary interest; γ_i is a random intercept for participant i that addresses the correlation in mobility across the two time points; and ε_{i1} and ε_{i2} are the residual error terms at baseline and follow-up, respectively.

This analysis will be repeated for each mobility parameter (gait speed, four stair ascent and descent time, supine to sit time), cognition scores (Trailmaking A and B, Stroop Color & Word score, and simple reaction time), and the Geriatric Depression Scale. The timed measures – Trailmaking A and B, and simple reaction time – will be inverse-transformed so that they have a speed interpretation; this will also reduce the influence of outliers. Similarly, all analyses will be repeated as stratified analyses (b - e below).

- b. Stratified according to < or > median age
- c. Stratified according to gender
- d. Stratified according to median years of education
- e. Stratified according to a clinical diagnosis of minor or major depression (for mobility and cognition)

3. Change in urinary severity index and depression category (based on the Geriatric Depression Scale) from baseline to 3 years. These analyses will be similar to the analyses for white matter hyperintensities in (1) and for mobility and cognition in (2), but using ordinal logistic regression.
 - a. According to treatment group (primary analysis)

$$\log(Y_{i1} > k / Y_{i1} \leq k) = \beta_{0k} + \beta_C x_i + \gamma_i$$

$$\log(Y_{i2} > k / Y_{i2} \leq k) = \beta_{0k} + \beta_C x_i + \beta_L + \beta_T x_i + \gamma_i$$

$$k = 1, \dots, m - 1$$

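### The primary regression of 36-month gait velocity leaves out baseline gait velocity, which is measured before randomisation; adding it would raise power at no data cost

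*Protocol*

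**What the plan says.** Protocol section 8.2, analysis a, sets the endpoint: "Gait velocity at T₃₆ is the primary outcome for hypothesis 1". The section calls this the primary efficacy analysis and says the trial is powered on it. The model is a multiple linear regression on treatment group, and "Age, sex, and 24 hour SBP at T₀ (baseline) will be included as covariates". The only other terms allowed are demographic factors on which the groups turn out not to be comparable.

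Section 8.3 powers the trial on the same three covariates: "A regression of gait velocity over 8 feet on our covariates age, sex, and 24 hour systolic BP at baseline" gave an R² of 0.1267.

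Section 5.6.2 lists the measurements at baseline visit 2, including "Mobility battery - Gait Speed, Stair ascent and descent, Supine-to-sit, Sit-to-stand". Randomisation follows that visit. Under Missing Data, section 8.2 adds that "our primary efficacy outcome analysis will be limited to participants who complete the study"; section 8.3 expects 140 of 200.

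Baseline gait is used in two other places. Protocol analysis c is a mixed model with the baseline value as one of the responses. SAP item 2a is a two-visit random-intercept model, applied to gait speed among other outcomes. It has a free parameter for "the difference in the average mobility score at baseline between the intervention group and the reference group" and no terms for age, sex or blood pressure. Item 2a carries the label of primary analysis, yet the SAP introduces its contents with "we have added several secondary analyses to be pre-specified with their rationale as needed".

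**The concern.** A patient's gait velocity at baseline can be expected to predict gait velocity three years later, probably better than age, sex and systolic pressure, which together explain about 13% of the variance in the prior cohort. The Précis describes the key mobility outcome as change from baseline, so baseline is clearly meant to count. The powered regression nevertheless leaves it out, and the clause on imbalanced demographic factors does not let it in, because gait speed is not a demographic factor. Hypotheses 2 and 3 have the same gap: baseline WMH and baseline FA and MD are not covariates for their own 36-month values.

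What is at stake is the precision of the main test. It rests on about 140 completers, and attrition above the projected 30% would take it below its power target. Randomisation makes treatment independent of baseline gait, so the omission does not bias the comparison of the arms.

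**Working it through.** **Inputs from the documents.** Section 8.3 gives 140 completers (70 per arm), a covariate R² of 0.1267, a detectable R² increase of 0.0533 (to 0.1800) and 85% power. For WMH it gives 0.1162, 0.0540 and 0.1702. Alpha is not stated; two-sided 0.05 is assumed, and it reproduces the plan's figure.

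**1. The plan's own figure.** This is the partial F test for one added regressor, with three covariates plus treatment.

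- f² = 0.0533 / (1 − 0.1800) = 0.0650
- noncentrality = 140 × 0.0650 = 9.10, with 1 and 135 degrees of freedom
- power = 0.850, as stated

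**2. Adding baseline gait.** Let r be the partial correlation of baseline with 36-month gait velocity, given age, sex and baseline 24-hour SBP. The documents do not give r, so it is assumed. The treatment effect is held fixed, the residual variance is multiplied by (1 − r²), and one degree of freedom is spent.

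- f² = 0.0533 / [0.82 × (1 − r²)], with 1 and 134 degrees of freedom
- the detectable difference shrinks by about √(1 − r²)

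| Assumed r | Power, 140 completers | Completers for 85% | Detectable difference, relative |
|---|---|---|---|
| not adjusted | 85.0% | about 140 | 1.00 |
| 0 | 85.0% | about 140 | 1.00 |
| 0.3 | 88.1% | 128 | 0.95 |
| 0.5 | 93.3% | 106 | 0.87 |
| 0.6 | 96.3% | 91 | 0.80 |
| 0.7 | 98.7% | 73 | 0.71 |

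At r = 0 the lost degree of freedom costs less than 0.01 percentage point of power. A simulation with random covariates and 70 patients per arm gave 87%, 92%, 96% and 98% for r = 0.3, 0.5, 0.6 and 0.7, within 2 points of the formula.

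**3. Fewer completers than planned.** With 120 completers the model as written has 79% power, against 89% with baseline gait at r = 0.5. With 100 completers the figures are 71% and 83%.

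**4. Hypothesis 2.** f² = 0.0540 / [0.8298 × (1 − r²)]. Power is 85.0% as written, then 88.1%, 93.3%, 96.3% and 98.7% at r = 0.3, 0.5, 0.6 and 0.7.

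**5. The SAP's model.** With a free baseline difference and completers only, item 2a is in effect a comparison of mean change. Let ρ be the within-arm correlation of the two visits and k the baseline SD divided by the 36-month SD. Its variance relative to adjusting for baseline as a covariate, with no other covariates in either model, is (1 + k² − 2kρ) / (1 − ρ²).

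| k | ρ = 0.5 | ρ = 0.8 |
|---|---|---|
| 1.0 | 1.33 | 1.11 |
| 0.8 | 1.12 | 1.00 |
| 1.2 | 1.65 | 1.44 |

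If patients with a baseline value only are kept (100 per arm at baseline, 70 at 36 months, k = 1, missing at random), the per-arm variance is (1 − ρ²)/70 + (1 − ρ)²/100. Divided by (1 − ρ²)/70, this gives 1.23 at ρ = 0.5 and 1.08 at ρ = 0.8.

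By the normal approximation, for the planned effect and k = 1, the change comparison has 80%, 95% and 99.3% power at ρ = 0.5, 0.7 and 0.8. Covariate adjustment has 90%, 98% and 99.7%.

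**The case against.** The strongest reply is that the plan is valid as it stands. It reaches its power target, it is unbiased, and baseline gait already enters analysis c and SAP item 2a. If item 2a governs, the gain is smaller than the move from 85% suggests: about 80% to 90% at ρ = 0.5, and almost nothing at high ρ when the baseline SD is 0.8 of the 36-month SD. That is correct. But the SAP describes its additions as secondary and nowhere withdraws the protocol's primary analysis. Covariate adjustment is also at least as efficient as item 2a in every case worked, and equal only at k = 0.8 and ρ = 0.8.

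Second, the size of the gain is assumed. Excluding patients with impaired gait (SPPB below 9) may narrow the range of gait speed and lower the correlation. The base R² comes from an 8-foot walk, while section 5.6 specifies an 8-metre course. These points stand: the direction is secure, the size is not.

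Third, at the effect seen in the prior cohort (R² increase 0.1082), the model as written already has f² = 0.1082 / (1 − 0.2349) = 0.141 and 99.3% power, so the covariate would add less than one point. This also stands. That effect is a selected observational contrast, however, and section 8.3 rests its case on finding smaller effects.

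Finally, a covariate makes up for lost numbers only. It does not resolve informative dropout, which the completer analysis leaves open.

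**Conclusion.** The point holds as an improvement that needs no new data. The primary model omits a baseline measure of its own outcome that is scheduled before randomisation. Adding it raises power from 85% to between 88% and 99% for assumed partial correlations of 0.3 to 0.7, or allows roughly 12 to 67 fewer completers at the same power (140 − 128 and 140 − 73). These figures assume two-sided 0.05, the planned R² increase and 140 completers. There is no bias to correct, the 85% is right for the model as written, and the downside at zero correlation is negligible. Separately, the labels in the protocol and SAP leave it unclear which gait model is the primary test, and that should be settled at the same time.

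**What to change.** In Protocol section 8.2, analysis a, add the baseline value of the outcome as a pre-specified covariate beside age, sex and baseline 24-hour SBP: gait velocity for hypothesis 1, WMH for hypothesis 2, and FA or MD for hypothesis 3. Let this fixed set replace the clause that admits demographic factors found to be imbalanced, so that the primary model does not depend on the data.

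In the SAP, state that the baseline-adjusted contrast in comfortable-pace gait speed at 36 months is the single primary test, and that the item 2a change model is supportive. If a longitudinal model with a common baseline mean (β_C = 0) is preferred for the continuous outcomes, fit it with an unstructured two-visit covariance and the same covariates. This reasoning does not extend to the ordinal models in SAP item 3.

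The cost is one degree of freedom per model, a stated rule for any missing baseline value, and matching amendments to protocol and SAP, with IRB approval, before database lock. No new data are needed.
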